8. RISKS AND BENEFITS

List all potential physical, psychological, social, financial or legal risks to subjects (risks listed here should be included on the consent form).

High Sugar Diet – There is minimal risk associated with consuming a high sugar diet for this duration. Each diet will be specifically catered to each subject, taking into account food preferences and any known food allergies. The diets are designed to be isocaloric and are not expected to change body weight. In the event of reported weight loss or reports of hunger, diets will be adjusted to increase energy intake. Unlike high amounts of glucose, 90% of dietary fructose intake is metabolized by the liver and does not substantially increase blood glucose levels²⁷; however, we do expect the high-sugar diet to raise plasma TGs and there is a possibility that it will also raise other cardiometabolic risk factors (e.g., LDL-cholesterol)²⁸⁻²⁹. We expect these parameters to return to baseline after participants return to their habitual diet. Moreover, there is no evidence that the short-term dietary changes proposed in this study influence long-term risk of cardiometabolic disease or cognitive impairment. Importantly, our high-sugar diet is representative of what a large number of adults in the United States are already consuming on a daily basis^{4,18}.

Venous Catheter/blood draw – Discomfort associated with insertion of the needle; local bleeding and a small hematoma (~10% of cases); risk of blood clot (~1% of cases); risk of infection of a hematoma or significant external blood loss (<1 in 1000); risk of fainting.

Genetic Risk for AD – One of the blood tests will determine whether or not the subject carries a gene that has been associated with risk for Alzheimer's disease (AD). People with this gene have a higher chance of developing AD compared with people who do not carry the gene. Some people who carry the gene may never develop AD. Others may develop AD even though they do not carry the gene. Subjects will be provided with the results of this test upon request only.

24-hour ABPM – There are no known risks associated with wearing the 24-hour blood pressure monitor. Subjects may find it irritating as it inflates regularly.

Acute Hypercapnia (CO₂ inhalation) – There are no risks associated with inhalation of small amounts of carbon dioxide. The hypercapnia protocol has been used in human studies clinically and in the research setting for decades without any adverse events. Study subjects may experience an increase

in heart rate, flushed skin, minor disorientation, or develop a mild headache during hypercapnia. Some subjects may notice a slight metallic taste when breathing the CO₂ gas mixture.

MRI Scan – MRI is an imaging technique that uses radio waves and magnetic fields to produce images of internal structures in the body. Unlike X-rays, the MRI does not use any ionizing radiation, and it does not use radioactivity, so there is no radiation related risks from having an MRI scan done. Below there is a description of MRI related risks and what is being done to reduce any possible risks associated with them:

- **Metal** – The MRI scanner produces a constant strong magnetic field, which may cause any metal implants, clips, or implanted medical devices within the body to shift position or malfunction. Subjects will be screened prior to entering the MRI scanner and those with implanted metal, clips or devices that are not MR-compatible will be excluded from this study. Metallic objects brought into the MRI environment can become hazardous projectiles and can also interfere with the data quality. To minimize this risk, subjects will be asked to remove all metal jewelry, belts with metal buckles, and all items from the pockets, including coins, electronics (including cell phones and hearing aids) and wallets. Some subjects may be asked to change into a gown if their clothing contains significant metal, including metal underwire bras.
- **Inner ear damage** – MRI scanning produces loud noises that can cause damage to the inner ear if appropriate hearing protection is not used. Subjects will wear earplugs and headphones to protect their ears.
- **Claustrophobia** – The subject's head will be centered inside a close-fitting scanning coil positioned in the bore of the scanner. If the subject feels anxious in confined, spaces they may not want to participate. If they are unsure, they can try the "mock" scanner at the MRI facility to evaluate their comfort level with the enclosed space of the magnet bore. If they decide to participate and begin to feel claustrophobic, they will be able to communicate with the research team via the intercom or the squeeze ball and the test will be discontinued.
- **Burns** – In rare cases, contact with the MRI transmitting and receiving coil, conductive materials such as wires or other metallic objects, or skin-to-skin contact that forms conductive loops may result in excessive heating and burns during the experiment. The operators of the MRI scanner will take steps, such as using foam pads when necessary, to minimize this risk. Tattoos with metallic inks can also potentially cause burns. Subjects will be instructed to let the MRI operator know immediately if they experience any heating or burning sensations during a scan. The scanning session will be stopped as soon as they tell the operator.
- **Nerve or muscle stimulation** – While the scanner is operating, there is a small chance that the rapidly changing magnetic fields could cause a slight tingling sensation or a muscle twitch, usually felt in the upper arms or torso. While these sensations may be startling, they are not dangerous or a health risk, and they have no lasting consequences. The sensations should stop when the scan ends. Because these sensations may nevertheless be distracting or even possibly uncomfortable, subjects will be instructed to squeeze the signal bulb to alert the scanner operator if they feel uncomfortable tingling or muscle twitching and we will immediately stop the scan. They will then have the opportunity to withdraw from the study or to continue.
- **Magnetic Resonance Elastography**: This study uses elastography to study the mechanical properties of the brain. Elastography uses low-amplitude (tens of microns) vibration at 50 Hz applied to the head to generate shear waves in the brain. Vibration is applied for less than 10 minutes of total duration. There is no known risk to vibration exposure at this amplitude, frequency, and time. However, it is possible the vibration may cause the subject to feel slight discomfort, and they will be instructed to alert the technologist via intercom or by squeezing the emergency ball if this occurs. The scan and vibration will be stopped immediately.

In your opinion, are risks listed above minimal* or more than minimal? If more than minimal, please justify why risks are reasonable in relation to anticipated direct or future benefits.

(*Minimal risk means the probability and magnitude of harm or discomfort anticipated in the research are not greater than those ordinarily encountered in daily life or during the performance of routine physical or psychological examinations or tests)

The risks associated with all procedures in this protocol are minimal and the magnitude of harm or discomfort are not greater than those encountered during similar procedures completed as part of routine clinical care (e.g., phlebotomy, MRI scanning). Although patients receiving a clinical MRI scan do not typically undergo the MRE and hypercapnia protocols, the overall risks and discomforts associated with these procedures are extremely low.

What steps will be taken to minimize risks?

The potential risks of the proposed study will be minimized by:

- using only safe, well-established procedures with only qualified and experienced personnel performing the procedures;
- having a registered dietitian prepare and package all food in a dedicated research kitchen;
- monitoring any gastrointestinal discomfort associated with consuming the diet;
- ensuring constant personal monitoring of each experimental session by the investigators;
- screening all participants for ability to undergo an MRI;

Describe any potential direct benefits to participants.

Because the risks of participating in this study are relatively small, the risk-to-benefit ratio also is relatively small. Subjects will receive benefits associated with overall knowledge of their health from the extensive testing performed for screening purposes and the established subject characteristics (i.e., blood glucose status, plasma lipids and lipoprotein profile, blood pressure, blood chemistries).

Describe any potential future benefits to this class of participants, others, or society.

The findings from the proposed research will provide important new information regarding the influence of dietary intake of added sugar on cardiovascular and brain health in midlife adults. In addition, the proposed research will also provide important insight into the potential mechanisms (e.g., TGs, inflammation) by which added sugar may negatively impact brain health. This information will contribute to the knowledge of how to prevent and treat cerebrovascular and cognitive impairment in midlife adults and may lead to future insight into preventing Alzheimer's disease risk.

If there is a Data Monitoring Committee (DMC) in place for this project, please describe when and how often it meets.

There is no DMC for this study.

9. COMPENSATION

Will participants be compensated for participation? Yes

If so, please include details.

Subjects will receive \$200 in total compensation for completing this study. They will receive \$100 for completing the first diet and \$100 for completing the second diet (including the laboratory visits). If they drop out after the screening visit (Visit 1.2), they will not be compensated because subjects will be receiving medical information from all of the screening tests free of charge. If they consume the prepared food and complete the 24-hour blood pressure monitoring but do not complete the laboratory visit, they will receive half the amount for that diet trial (\$50); however, if this occurs during the first diet, the investigators reserve the right to terminate the subject depending on the reason for not completing the laboratory visit. Compensation does not include travel time, but upon request will compensate subjects for their travel mileage, at the current IRS approved mileage rate.

Compensation is based on completion of study visits, not individual procedures. Subject can be compensated an additional \$20 for each subject referral that is consented into this study. Table 10.1 outlines the total compensation for each visit is presented below.

Table 10.1 Compensation Schedule

	Visit #	Duration	Purpose	Total
Phase 1	Visit 1.1 & 1.2	2.5 hr	Informed Consent & Screening Measures	No compensation Subjects receive free health information
Phase 2	Visit 2.1	2 hr	Vascular and Cognitive Function	\$50 (only if visit 3.2 & 3.3 is not completed)
	Visit 2.2	1.5 hr	MRI	
Phase 3	Visit 3.1	30 min	Diet Pick-Up	\$100
	Visit 3.2	2 hr	Vascular and Cognitive Function	
	Visit 3.3	1.5 hr	MRI	
Phase 4	Visit 4.1	30 min	Diet Pick-Up & Blood Draw	\$100
	Visit 4.2	2 hr	Vascular and Cognitive Function	
	Visit 4.3	1.5 hr	MRI	
Total Duration		14 hr	Total Compensation	\$200

10. DATA

Will subjects be anonymous to the researcher? No.

If subjects are identifiable, will their identities be kept confidential? (If yes, please specify how)

Subjects will not be individually identified, except by a subject ID number known only to the investigators.

How will data be stored and kept secure (specify data storage plans for both paper and electronic files. For guidance see <http://www.udel.edu/research/preparing/datasstorage.html>)

Physical data will be stored in a locked file cabinet in the PI's lab space and will only be accessible by

members of the research team. Physical data that are transcribed into an electronic database, and electronically captured data will be kept on a password protected laboratory server that is maintained by the University of Delaware. Electronic data will be periodically backed-up onto an external hard drive that will be kept in a locked office space. All of the ultrasound images and files generated by the SpphygmoCor and RespirAct devices will be coded with an identification number and will not contain the name of the subject. The names of subjects will not be identified in any publication arising from these studies. Only the PI and research staff will have access to data from this study.

How long will data be stored? All data will be stored in a locked cabinet or a password protected computer indefinitely.

Will data be destroyed? YES NO (if yes, please specify how the data will be destroyed)

Will the data be shared with anyone outside of the research team? YES NO (if yes, please list the person(s), organization(s) and/or institution(s) and specify plans for secure data transfer)

The data may be shared with the National Institutes of Health. The trial will be registered with clinicaltrials.gov once the funding is finalized; however, only de-identified data will be reported.

How will data be analyzed and reported?

Data will be aggregated and reported as group means or as de-identified, individual data points. Because this study is intended to support a larger R01 proposal, we will analyze the data after the first 5-10 subjects have completed all testing. If we do not observe any effect of the diet on primary outcomes, we will consider amending the protocol to increase the duration of the controlled feeding window and/or modify the composition of the diets. Any subjects tested prior to a major amendment of the protocol will be replaced to achieve the target sample size.

11. CONFIDENTIALITY

Will participants be audiotaped, photographed or videotaped during this study?

Subjects will be audiotaped for the purpose of analyzing their memory tests after each visit. These recordings will be deleted immediately after the test has been scored.

How will subject identity be protected?

Information obtained from this study will be kept strictly confidential. Subjects will not be individually identified, except by subject number, known only to the investigators. All data stored as paper files or digitally will be kept indefinitely. The paper files are stored in a locked cabinet. While the results of the research may be published, subjects' names and identities will not be revealed.

Is there a Certificate of Confidentiality in place for this project? (If so, please provide a copy).

This study is (pending) funding from NIH which automatically issues a CoC per the notice of award.

12. CONFLICT OF INTEREST

(For information on disclosure reporting see: <http://www.udel.edu/research/preparing/conflict.html>)

Do you have a current conflict of interest disclosure form on file through UD Web forms?

Yes.

Does this project involve a potential conflict of interest*?

* As defined in the [University of Delaware's Policies and Procedures](#), a potential conflict of interest (COI) occurs when there is a divergence between an individual's private interests and his or her professional obligations, such that an independent observer might reasonably question whether the individual's professional judgment, commitment, actions, or decisions could be influenced by considerations of personal gain, financial or otherwise.

If yes, please describe the nature of the interest:

13. CONSENT and ASSENT

Consent forms will be used and are attached for review (see Consent Template under Forms and Templates in IRBNet)

Additionally, child assent forms will be used and are attached.

Waiver of Documentation of Consent (attach a consent script/information sheet with the signature block removed).

Waiver of Consent (Justify request for waiver)

14. Other IRB Approval

Has this protocol been submitted to any other IRBs?

If so, please list along with protocol title, number, and expiration date.

15. Supporting Documentation

Please list all additional documents uploaded to IRBNet in support of this application.

Informed Consent Form

Screening and Control Measures – *the uploaded forms are examples only and the format may be modified for online administration via REDCap.*

- COVID19 Form
- Daily Appetite Survey
- Diet Recall Form
- Family History
- Food Preference Form
- Intake and Demographics Form
- International Physical Activity Questionnaire (IPAQ)
- Medical History Form

- Menstrual History Form
- Modifiable Activity Questionnaire (MAQ)
- MRI Screening Form
- Munich Chronotype Questionnaire
- Pittsburgh Sleep Quality Index (PSQI)
- PHQ-9 Depression Survey
- PROMIS-57 Profile v2.1

Outcome Measures – *the uploaded forms are examples only and the format may be modified for online administration via REDCap or using an iPad (e.g., NIH Toolbox)*

- Brief Visuospatial Memory Test (BVMT-R)
- Hopkins Verbal Learning Test (HVLT-R)
- NIH Toolbox
 - o Pattern Comparison Processing Speed Test
 - o Flanker Inhibitory Control Test

Advertisements

- novaLab_Sugar Feeding Study_Email and Mailed Letter
- novaLab_Sugar Feeding Study_Recruitment Flyer

Cover Page for Statistical Analysis Plan

Official Title: The effects of added sugar intake on brain blood flow and hippocampal function in midlife adults

ClinicalTrials.gov ID: NCT05211726

Protocol ID: 1760500

Date of Document: September 23, 2020

Statistical Analyses

The aims for this study will be tested using General Linear Modeling. For hypotheses H1a and H2a, a Profile Analysis (multivariate within-in subjects ANOVA) will be performed. If the omnibus test is significant, univariate within subject ANOVAs will be performed, testing the effect of diet (baseline, low sugar, and high sugar diets) on each outcome. The multivariate extension is being used to control for type-I error inflation that might occur because each aim has three primary outcomes (Aim 1: 24-hour SBP, arterial compliance, and cerebrovascular reactivity; Aim 2: HC stiffness, HC damping ratio, and delayed recall memory). All assumptions for these models will be tested, and data will be screened for outliers and influential cases. Assumptions of linearity, sphericity, and normality will be evaluated using Box-Cox, Mauchly's, and Shapiro-Wilk tests, respectively. Because some values are expressed as ratios, if the assumptions of the within subject's ANOVA cannot be satisfied by transformations suggested by the Box-Cox test then either the non-parametric Friedman test or a Generalized Linear Model will be used. Given the cross-over design, the order effect will be tested using the same model but the effect will just be time point (baseline, post diet 1, and post diet 2). If significant, the order effect will be included in the final model. A significant diet effect will be followed by pairwise comparisons using Fisher's LSD procedure. The alpha is set at 0.05 for each test. Exploratory analyses will be conducted for hypotheses H1b and H2b, using regression models testing the changes (from baseline) in each primary outcome from Aims 1a and 2a after the high sugar diet with the changes in TGs, markers of oxidative stress, and inflammation. Additionally, regression models will be used to explore whether changes in the primary outcomes from Aim 1 moderate the relation between the changes in the primary outcomes in Aim 2. This moderation will be tested by including the interaction effects of changes in outcomes from Aim 1 and 2 with the changes in TGs, markers of oxidative stress, and inflammation. During Year 2, the PI will work with the COBRE Core's lead biostatistician ([name]) to conduct an interim data analysis for an R01 proposal. The O'Brien-Fleming alpha boundary function will be used, the alpha for significance of the interim analysis is .0054 and for the final analysis is .0492.

Randomization, Blinding, Power & Sample Size

To enhance scientific **rigor and reproducibility**, subjects will be randomized to diet order with Group A receiving the high sugar diet first followed by the low sugar diet and Group B receiving each diet in the opposite order. Investigators responsible for data collection or analysis will be blinded to treatment condition. To address **sex as a biological variable**, we will use a block randomization scheme to ensure an even number from each sex within each treatment group and will covary for sex in our analyses. A major objective is to generate preliminary data and conduct a power analysis for an eventual R01. Power for this pilot study was determined for the profile analysis for Aims 1 and 2, testing the change across the three measurement occasions for three outcomes. This study is adequately powered (power = .80), with n=30 to detect a moderate effect ($d=.46$), for three outcomes and three timepoints with nominal alpha (.05), assuming a conservative correlation among the outcomes and repeated measures of 0.3. If the multivariate test is significant, this study is adequately powered (power = .80), with n=30 to detect a moderate effect ($d=.56$), for three timepoints with nominal alpha (.05), assuming a correlation among the repeated measures of 0.3 for follow-up univariate within subject ANOVAs. To account for drop-out or experimental error, our total recruited sample size will be 40. This effect size matches ones seen in the literature, which found a moderately large effect ($d = 0.69$ with $n=14$) in the effect of increased serum TGs within 4-5 days of a high fructose meal⁷⁵.

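### After a failed sphericity test the SAP leaves an open choice between Friedman and a Generalized Linear Model; it names no corrected F, and the Friedman branch cannot carry the time-point term

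*SAP*

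**What the plan says.** All of this is in the SAP, mostly under Statistical Analyses.

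- The univariate follow-up is a within-subject ANOVA with three levels, "testing the effect of diet (baseline, low sugar, and high sugar diets) on each outcome".
- The checks are fixed: "Assumptions of linearity, sphericity, and normality will be evaluated using Box-Cox, Mauchly's, and Shapiro-Wilk tests, respectively".
- The fallback is conditional. Only "if the assumptions of the within subject's ANOVA cannot be satisfied by transformations suggested by the Box-Cox test" does the next step apply: "then either the non-parametric Friedman test or a Generalized Linear Model will be used". No criterion separates the two options, and neither Greenhouse-Geisser nor Huynh-Feldt is mentioned.
- Order is tested with time point (baseline, post diet 1, post diet 2) as the effect. "If significant, the order effect will be included in the final model".
- On pairwise comparisons: "A significant diet effect will be followed by pairwise comparisons using Fisher's LSD procedure". With three levels these include HS against LS.
- Under Randomization, Blinding, Power & Sample Size, the team "will covary for sex in our analyses".

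**The concern.** Sphericity concerns the variances of the differences between occasions. A Box-Cox transformation acts on the scale of a single variable and is not designed to equalise those variances. An outcome that fails only Mauchly's test can therefore pass through the Box-Cox step unrepaired and reach the fallback, although the usual answer is to correct the degrees of freedom of the F test.

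Three things are then at stake.

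1. The method for a primary outcome would be chosen after its data are seen, outcome by outcome, across six primaries.
2. If Friedman is chosen, a significant time-point effect has nowhere to go, because the standard test takes no covariates. The SAP would contradict its own rule on order.
3. On near-normal data, ranking within three occasions gives up power that a 30-to-40-subject crossover can ill afford.

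**Working it through.** **Inputs from the SAP.** n=30, 40 recruited, three timepoints, correlation 0.3, d=0.56, alpha 0.05, stated power 0.80 for the univariate ANOVA.

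**Assumed, because the documents give no figures.** The non-spherical covariances, the error shapes and the size of any visit shift. Simulations used 4,000 to 20,000 trials per scenario. Ranges below are across independent runs.

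**1. The SAP's own figure.** With f = d/2 = 0.28, the noncentrality is f²·n·m/(1−ρ) = 0.0784 × 30 × 3 / 0.7 = 10.08 on 2 and 58 df. Power is 0.797, so the stated 0.80 reproduces.

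**2. Friedman's efficiency under normality, k=3.** (3/π) × k/(k+1) = 0.955 × 0.75 = 0.716. Thirty subjects act like 30 × 0.716 = 21.5. Matching 30 would take 30/0.716 = 41.9, more than the 40 to be recruited.

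**3. Two ways to place the effect.** If LS and HS move by −0.28 and +0.28 from baseline, HS-LS is 0.56 and f = 0.56/√6 = 0.229. The SAP's f = 0.28 needs shifts of ±0.28 × √1.5 = ±0.343, so HS-LS is 0.686. Both are shown.

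**4. The paired contrast by hand (HS-LS 0.56).**
- Spherical: variance of the difference 2 × (1−0.3) = 1.4, SD 1.183. Then 0.56/1.183 × √30 = 2.59, giving power of about 0.71.
- Non-spherical (HS SD 1.5, LS-HS r=0.8, baseline r=0.3): 1 + 2.25 − 2 × 0.8 × 1.5 = 0.85, SD 0.922. Then 0.56/0.922 × √30 = 3.33, giving about 0.89.

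**5. Power on normal data.**

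| Scenario | Friedman | Greenhouse-Geisser F | Paired HS-LS t |
|---|---|---|---|
| Spherical, HS-LS 0.56, opposite shifts, n=30 | 0.49–0.51 | 0.60–0.61 | 0.71 |
| Same, n=40 | 0.59–0.61 | 0.74–0.75 | 0.83–0.84 |
| Spherical, SAP calibration f=0.28, n=30 | 0.66 | 0.79 | 0.87 |
| Spherical, only HS moves by 0.56, n=30 | 0.60–0.61 | 0.73–0.74 | 0.70–0.71 |
| Non-spherical as in step 4, n=30 | 0.63 | 0.54–0.55 | 0.89–0.90 |
| HS SD 1.8, f=0.28, n=30 | 0.40 | 0.46 | 0.53 |
| LS-HS r=0.7, others 0.1, f=0.28, n=30 | 0.91 | 0.84 | 0.996 |

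**6. Power on non-normal, spherical data (f=0.28, n=30).**

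| Error shape | Friedman | Greenhouse-Geisser F | Paired t | Wilcoxon on HS-LS |
|---|---|---|---|---|
| t with 3 df | 0.91 | 0.82 | 0.88 | 0.96 |
| 10% contaminated normal | 0.91 | 0.78 | 0.86 | 0.94 |
| Lognormal | 0.98 | 0.77 | 0.85 | 0.96 |

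The lognormal row omits the Box-Cox step, so it flatters Friedman.

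**7. No diet effect, third-visit shift of 0.5 / 0.8 SD (n=30, r=0.3).**
- Friedman rejects in 14–15% / 28–30%.
- Unadjusted Greenhouse-Geisser F: 15–18% / 32–33%.
- Unadjusted paired HS-LS t: 3% / 2%. The shift cancels in the mean but inflates the SD.
- Period-adjusted HS-LS contrast: about 5% in both.

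Both three-level tests inflate because baseline is always the first occasion and is a level of the factor. A later-visit shift then looks like a difference between baseline and the diets. For the same reason, once time point enters the model, only HS-LS remains estimable as a diet effect.

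**The case against.** The strongest reply is that the plan already has an adjusted route. Box-Cox is tried first, and the Generalized Linear Model can carry both order and sex. This stands. A reader might infer that any outcome failing Mauchly or Shapiro-Wilk goes to Friedman, but the documents say only that it may. For the same reason the chance that Mauchly flags at least one of six spherical outcomes (1 − 0.95⁶ = 26%, if independent) is a flag rate, not a rate of analysis by Friedman.

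Other stronger readings also fail:

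- *That HS-LS is never tested.* Fisher's LSD includes it, after a significant diet effect.
- *That Friedman is generally weaker.* Steps 5 and 6 show it beating the corrected F under two non-spherical patterns, and beating both the corrected F and the paired t with heavy tails or skew. A corrected F also does nothing for a normality failure.
- *That the false-positive rates in step 7 are peculiar to Friedman.* An unadjusted corrected F does no better.
- *That losing the sex covariate matters.* A sex main effect cancels within subject, in Friedman as in the ANOVA, and the SAP asks for no sex-by-diet term.
- *That order is always required.* It enters only if significant.

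It is also fair to say that this is a pilot meant to yield preliminary data. That limits the consequence but does not supply the missing rule.

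**Conclusion.** The point holds in limited form. For an outcome that fails Mauchly's test, the SAP offers a transformation that does not address sphericity, then an undecided choice between two methods, one of which cannot hold the SAP's own time-point term. No sphericity-corrected F is named.

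What matters most for error control is the period term: about 14% or 30% false rejections without it in a three-level test, against about 5% for the period-adjusted HS-LS contrast. These rates rest on assumed shifts of 0.5 and 0.8 SD at the third visit.

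On near-normal, spherical data Friedman costs about 10 power points against the corrected F and about 20 against the paired contrast (0.50, 0.60, 0.71). In the assumed non-spherical case the figures are 0.63, 0.55 and 0.89, so the gain there comes from the HS-LS contrast and not from the corrected F. No general power loss is claimed for non-normal data.

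**What to change.** Replace the open fallback with a fixed rule.

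1. **Mauchly's test fails:** use the Greenhouse-Geisser-corrected F for the three-level test. Take HS-LS from each subject's difference, with its own variance and a period (diet-order) term. In practice, average the mean difference of the two order groups, so that a period shift cancels.
2. **Normality still fails after transformation:** use a rank or permutation test on the period-adjusted HS-LS difference, in place of Friedman or the Generalized Linear Model. In step 6 an unadjusted Wilcoxon on HS-LS scored 0.94–0.96 against 0.91–0.98 for Friedman, so little is lost.

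The cost is SAP wording only, with no change to visits, measurements or sample size. The one drawback is that under some non-spherical patterns the corrected three-level F has less power than Friedman; in those simulated the HS-LS contrast more than makes this up.
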